7.1. Does the project involve genetic testing? **Not Applicable, SKIP TO SECTION 8**

7.2. Will specimens be kept for future, unspecified use? Choose an item.

7.3. Will samples be made anonymous to maintain confidentiality? Choose an item. (*If there is a link, it is not anonymous. Coding is not anonymous.*)

7.4. Will specimens be destroyed after the project-specific use is completed? Choose an item.

7.5. Will specimens be sold in the future? Choose an item.

7.6. Will subjects be paid for their specimens now or in the future? Choose an item.

7.7. Will subjects be informed of the results of the specimen testing? Choose an item.

7.8. Are there any implications for family members based on specimen testing results? Choose an item.

7.8.1. If answer to section 7.8 is yes, they may be participants.

7.9. Will subjects be informed of results obtained from their DNA? Choose an item.

7.10. Explain if the study is looking for an association between a genetic marker and a specific disease or condition, but at this point it is not clear if the genetic marker has predictive value.

7.11. Describe if the study is based on the premise that a link between a genetic marker and a specific disease or condition is such that the marker is clinically useful in predicting the development of that specific disease or condition.

7.12. Will the subject be notified of the results and the provision for genetic counseling? Choose an item.

Section 8: International Research

8.1. Does this study involve international research? NOT APPLICABLE If no, go directly to section 9.

8.1.1. For further instructions, refer to [VHA Directive 2005-050, Requirements for Conducting VA-Approved International Research Involving Human Subjects, Human Biological Specimens, or Human Data](#)

8.1.2. *VHA Handbook 1200.05 definition of international research - VA international research is any VA-approved research conducted at international sites (not within the United States (U.S.), its territories, or Commonwealths); any VA-approved research using either human biological specimens (identified, de-identified, or coded) or human data (identified, de-identified, or coded) originating from international sites; or any VA-approved research sending such specimens or data out of the U.S. NOTE: For the purposes of the VHA Handbook 1200.05, research conducted at U.S. military bases, ships, or embassies is not considered international research.*

Section 9: Statistical Analysis

9.1. Include statistical power calculations and the assumptions made in making these

calculations.

Aim 1: A meta-analysis of 39 physiotherapy and exercise intervention trials in PD estimated an effect size (mean(SD)) of a 5.0(7.3) point improvement in UPDRS motor score comparing intervention to control groups (6). This change in UPDRS motor score corresponds to a “moderate clinically meaningful difference” as described by Shulman and colleagues(100). Using a two-sample t-test with 80% power, we need 35 subjects per group to detect this difference between the control and intervention groups. Accounting for 20% drop-out, we would need 44 subjects per group. Recent studies completed by [name] and EMU staff include 2 community-based weightlifting interventions lasting 52-weeks with drop-out rates of 8% (N=141 randomized) and 14% (N=154 randomized)(101, 102). A two-year trial with a similar intervention had a drop-out rate of 13% (N=164 randomized) (103). EMU staff and protocols have been very successful in promoting retention in long-term exercise trials. The drop-out rate assumed for this aim may be an over-estimate for the short-term intervention but allows recruitment to adequately power the long-term intervention in Aim 2, as well. Based on our preliminary data that approximately 50% of DIP subjects have olfactory deficits and that hyposmia is strongly predictive of abnormal DaT (we will assume 75% of subjects with hyposmia will have DaT SPECT abnormalities), we anticipate screening approximately 250 DIP subjects with olfactory tests to achieve the required cohort size. Olfactory screening with the UPSIT is straightforward and can be completed in 15-20 minutes.

Aim 2: Because DaT SPECT signal loss is most sensitively detected in the putamen (particularly posterior putamen) in early PD, we will use this region to power our analysis. In our analysis of longitudinal DaT SPECT data from the PPMI study, average putamen signal was 0.83 (0.30) at baseline and 0.68 (0.23) at year 1 (absolute change 0.15 (0.13)), representing the expected change in the non-intervention group. With 35 subjects per group expected to complete the study (accounting for 20% drop-out), we are able to detect at least 0.06 points difference of change in average putamen signal between intervention and control groups (i.e., control group changes by 0.15 and intervention group changes by 0.09) with 80% power using two-sample t-test (alpha=0.05). As described in our preliminary data, the rate of rate of striatal degeneration during the prodromal period that we will capture may be greater than what been reported for the clinically manifest period of PD. Thus, the above estimates of the required sample size are conservative and it is likely that we could detect a significant effect of the intervention even if fewer than projected subjects complete the intervention (owing to greater attrition or decreased recruitment). For example if the non-intervention change in DaT uptake is 10% higher than we assumed (0.165 vs. 0.15), we could detect a similar effect size of the intervention with 29 (rather than 35) subjects per group. If the rate were 20% higher, we could detect a similar effect with 24 subjects. If the baseline rate of decline were 0.2 rather than 0.15 (33% higher), we could detect the effect with only 20 subjects per group.

Aim 3: One study has measured BDNF levels in PD patients before and after an 8 week exercise intervention(28). Baseline levels were mean (SD) 21 (3.4) and average post-intervention levels were 25(6.4) in the intervention group with no significant change in the non-intervention group. With 35 subjects per group expected to complete the study (accounting for 20% drop-out), we are able to detect a 4 point difference of change in BDNF between intervention and control groups using two-sample t-test with 80% power (alpha=0.05). This calculation assumes a conservative estimate of SD of change in the above calculation (SD=6.4, the largest SD of outcome in the above study).

9.2. Define plans for data and statistical analysis, including key elements of the statistical plan, stopping rules and endpoints.

Aim 1: The primary outcome of this aim is comparison of the change in average UPDRS motor scores between the exercise and no intervention groups after 8 weeks. Between groups changes will be assessed with a two (independent) sample t-test. Secondarily, within group changes from baseline for UPDRS scores and quantitative assessments will be assessed using paired t-tests. Additionally, the relationship between change in fitness (Vo2max) and change in UPDRS scores will be assessed using partial correlations controlling for age, gender and baseline fitness levels. An intention-to-treat analysis will be applied primarily but pre-planned secondary analyses will compare only exercise subjects deemed compliant with controls.

Aim 2: The primary outcome of this aim is comparison of the change in semi-quantitative DaT uptake from scans at baseline and 52 weeks (post-intervention). Because DaT SPECT signal loss is most sensitively detected in the putamen (particularly posterior putamen) in early PD(69), we will focus the primary analysis on this region, though we will also examine signal changes in the caudate, anterior putamen and an index of right/left asymmetry. Differences in the rate of DaT signal change between groups will also be assessed using linear mixed-effects models which will allow us control for the influence of age, gender or other confounders. Linear mixed-effects modelling also accommodates the inclusion of data points with different follow-up times, allowing the analysis to include all subjects even if they do not complete the full intervention period. In this analysis, we will determine whether there is a significant effect of the “treatment group x time” interaction (rate of change) on the predictive value of models with DaT uptake as the dependent variable. An intention-to-treat analysis will be applied primarily but pre-planned secondary analyses will compare only exercise subjects deemed compliant with controls.

Aim 3: The primary outcome of this aim will be differences in the rate of change between intervention groups as assessed using independent samples t-tests. A secondary outcome will examine the rate of change using linear mixed-effects models controlling for age, gender and other potential confounders. Additionally, relationships of biomarkers to VO2max, UPDRS, quantitative motor and quantitative DaT will be examined using partial correlations controlling for age and gender.

9.3. Provide sample size determination and analysis (include anticipated rate of screen failures, study discontinuations, lost to follow-up, etc.)

Based on power calculations, we anticipate screening 250 DIP subjects with olfactory testing, with the expectation that approximately 125 (50% of those screened) will be included in the imaging cohort, 88 (75% of those with abnormal olfactory testing) will be enrolled in exercise cohort and approximately 70 (assuming a 20% drop-out rate) will complete the study. 2018 Amendment: We anticipate enrolling 56 additional subjects under the modified inclusion criteria with 48 (24 per group) expected to complete all study activities. This will still allow for meaningful analysis of our primary outcomes according to the sensitivity analysis of sample size from the original protocol (20 per group adequate).

9.4. Describe how, where and by whom the data will be analyzed.

Preliminary statistical analyses will be conducted by the PI in the CMC PADRECC. Coded data will also be analyzed by [name], Associate Professor of Biostatistics at Penn and statistical advisor on [name] CDA award. [name] will have no access to the code that relates subjects' PHI to their study data

Section 10: References - Bibliography of cited literature

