Patients aged 40-89 with a clinical diagnosis of DIP will be recruited from the CMC VAMC PADRECC and Behavioral Health Service (BHS) clinics. We will recruit subjects with parkinsonian signs (rest tremor, rigidity, bradykinesia) occurring after the institution of therapy with a antipsychotic medication having known dopamine receptor blocking activity (examples include haloperidol, chlorpromazine, fluphenazine, perphenazine, risperidone, thioridazine, thiothixene, ziprasidone, olanzapine and aripiprazole). Potential subjects with DIP will be pre-screened using a brief (12 item) scratch and sniff smell test with hyposmic subjects invited to learn more about the study (see script). Brief olfactory testing should be completed in 5-10 minutes. We anticipate screening 250 subjects with olfactory testing. Approximately 120 subjects will undergo baseline assessment including DaT-SPECT as described above. Subjects with abnormal DaT-SPECT will be invited to be randomized into the exercise study. In addition to the screening described above, we will invite subjects from [name] CPPF pilot study "Degenerative nigrostriatal dysfunction in drug-induced parkinsonism" PROM#01481 who have abnormal DaT-SPECT to enroll in the present protocol. These subjects will have explicitly agreed to future contact for related studies in the ICF for PROM#01481. We may also invite subjects identified by their PADRECC provider who had DaT-SPECT (with an abnormal result) performed clinically outside of a research protocol within the prior 3 months and agree to be contacted. We will randomize 88 subjects to either exercise intervention or no intervention and anticipate that 70 subjects will complete all aspects of the study. Additionally, letters will be sent to potential participants letting them know that they may be eligible for a study with a brief description of the study and give them a number of they would like to learn more or to request no further contact. 2018 Amendment: We anticipate enrolling 56 additional subjects under the modified inclusion criteria with 48 (24 per group) expected to complete all study activities. This will still allow for meaningful analysis of our primary outcomes according to the sensitivity analysis of sample size from the original protocol (20 per group adequate).

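### Aim 2 power: the plan's own inputs give about 48% power for a 0.06 difference with 35 per group, not 80%, and the 2018 claim that 20 per group is adequate rests on the same unreconciled figures

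*Combined protocol and SAP*

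**What the plan says.** Section 9.1 (Aim 2) takes its planning values from longitudinal PPMI data. Average putamen signal falls from 0.83 (0.30) at baseline to "0.68 (0.23) at year 1 (absolute change 0.15 (0.13)), representing the expected change in the non-intervention group". With 35 completers per group after 20% drop-out, the section states that "we are able to detect at least 0.06 points difference of change in average putamen signal between intervention and control groups", spelled out as "i.e., control group changes by 0.15 and intervention group changes by 0.09) with 80% power using two-sample t-test (alpha=0.05".

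It calls these estimates conservative because prodromal decline may be faster, and adds three cases. If the untreated decline is 0.165, "we could detect a similar effect size of the intervention with 29 (rather than 35) subjects per group". If it is 20% higher (0.18), 24 are said to suffice. If it is 0.20, "we could detect the effect with only 20 subjects per group".

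The 2018 amendment text in Sections 5.1.3 and 9.3 expects 24 completers per group. It says: "This will still allow for meaningful analysis of our primary outcomes according to the sensitivity analysis of sample size", citing the "sensitivity analysis of sample size from the original protocol (20 per group adequate").

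For Aim 3, Section 9.1 says that with 35 per group "we are able to detect a 4 point difference of change in BDNF between intervention and control groups using two-sample t-test with 80% power", using an SD of 6.4.

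**The concern.** Difference, SD, group size, test, alpha and power are all given for Aim 2, so the claim can be checked directly, and the six figures cannot all be true. Aim 2 is the disease-modification question. As written, a reader cannot tell whether the trial was sized for a 40% or a 60% slowing of signal loss.

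The problem carries forward, because the amendment defends a smaller number of completers with the sensitivity figures. It also drops the condition attached to 20 per group in Section 9.1, a decline of 0.20 rather than 0.15. Someone who believes the trial had 80% power for a 40% slowing would read too much into a null result.

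**Working it through.** **Inputs (Section 9.1, Aim 2).** Difference δ = 0.15 − 0.09 = 0.06; SD of change 0.13; n = 35 per group; two-sample t-test; alpha 0.05. Sidedness is not stated, so two-sided is assumed.

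**Formula.** SE = SD × √(2/n); noncentrality λ = δ/SE; df = 2(n − 1). Power is the probability that a noncentral t with these values exceeds the two-sided 5% critical value in absolute size.

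**Method check on Aim 1.** With 5.0, SD 7.3 and n = 35, power is 80.6%, as the plan states. The method therefore matches the plan's where the plan is consistent.

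**Aim 2 as stated.** SE = 0.13 × √(2/35) = 0.0311; λ = 0.06/0.0311 = 1.93; df = 68. Power is **47.8%**, against 80% stated.

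- Rounding of the SD (0.125 to 0.135): 51% to 45%.
- One-sided alpha 0.05: 60.5%.
- All 44 randomised per group analysed: 57.2%.
- n per group for 80% power at 0.06: 75.
- Difference detectable with 80% power at n = 35: 0.0883, and 0.0883/0.15 = 59% slowing.

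**Sensitivity cases, SD 0.13.** The phrase about a similar effect size is read here as a constant proportional slowing, which is an assumption.

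| Decline | Plan's n | 40% slowing: δ | n for 80% | Power at plan's n | 60% slowing: δ | n for 80% | Power at plan's n |
|---|---|---|---|---|---|---|---|
| 0.15 | 35 | 0.060 | 75 | 47.8% | 0.090 | 34 | 81.5% |
| 0.165 | 29 | 0.066 | 62 | 47.6% | 0.099 | 29 | 81.3% |
| 0.18 | 24 | 0.072 | 53 | 46.8% | 0.108 | 24 | 80.4% |
| 0.20 | 20 | 0.080 | 43 | 47.5% | 0.120 | 20 | 81.2% |

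The plan's 29, 24 and 20 are exactly the 60%-slowing sizes. That suggests the difference (0.09) and the remaining change (0.06) were exchanged, but this is an inference. A 40% slowing with SD near 0.087 gives the same sizes, because 0.06/0.0867 = 0.09/0.13 = 0.69. No such SD is stated.

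**The amendment's numbers, decline 0.15, SD 0.13.**

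| n per group | Power for 0.06 | Power for 0.09 | Detectable difference (80%) |
|---|---|---|---|
| 24 | 34.7% | 65.1% | 0.107 (72% of 0.15) |
| 20 | 29.6% | 56.9% | 0.118 (79% of 0.15) |

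The 24-per-group row assumes those completers are analysed alone; the documents do not say.

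**Aim 3.** With 4/6.4 and n = 35, power is 73.2%; the difference detectable with 80% power is 4.35.

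**The case against.** The headline figure is not open to dispute; the stated inputs do not give 80%. The fair objections concern what is built on it.

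- **Analysis method.** Section 9.2 names no t-test for Aim 2 and plans mixed models adjusted for age, gender or other confounders. A baseline-adjusted analysis could do better. The stated SDs imply a correlation of (0.30² + 0.23² − 0.13²)/(2 × 0.30 × 0.23) = 0.913 and a residual SD of 0.23 × √(1 − 0.913²) = 0.094. Power for 0.06 at n = 35 is then about 75% (65-86% over rounding of the inputs). This stands as a limit on the 48%, but the plan does not state baseline adjustment, and Section 9.1 bases its claim on the t-test.
- **Pooling.** The amendment speaks of 56 additional subjects. If they are pooled with those already randomised, the 24-per-group figures do not describe the final analysis. This stands, so those figures must carry that condition. The amendment itself, however, sets 24 per group against the 20 it calls adequate.
- **The 60% reading.** The plan nowhere states a 60% slowing, and the similar-effect wording is ambiguous. If the exercise arm is held at 0.09 while the control decline is 0.20, the difference is 0.11 and 20 per group gives 74%, still below 80%. Only the sponsor knows what was intended.
- **Faster prodromal decline.** Section 9.1 argues for this, and it could offset smaller numbers. It does not repair the arithmetic at 0.15, and the current inclusion criteria also admit clinically diagnosed PD.

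**Conclusion.** The concern holds. On the plan's stated inputs, Aim 2 has about 48% power for a 0.06 difference, some 32 points below the claim, and 80% power only for about 0.088. This rests on SD of change 0.13, an unadjusted two-sided t-test and 35 analysed per group. The sensitivity sizes deliver 80% only under an effect or an SD that the plan does not state.

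At the assumed decline of 0.15 and SD 0.13, neither a 40% nor a 60% slowing reaches 80% power with 24 or 20 per group. The unqualified statement that 20 per group is adequate is therefore not supported. Which input went wrong cannot be settled from the documents. The Aim 3 shortfall (73% against 80%) is real but minor.

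**What to change.** 1. **Section 9.1, Aim 2.** State that 35 per group with SD of change 0.13 gives 80% power for about 0.088 and about 48% for 0.06, and say which effect was intended.
2. **Sensitivity cases.** If a 40% slowing was meant, give 62, 53 and 43 per group, or report about 47-48% power at 29, 24 and 20. If a 60% slowing was meant (0.15 against 0.06), say so and keep 29, 24 and 20 for that effect. If another SD was used, state it and its source.
3. **Sections 5.1.3 and 9.3.** Replace the adequacy statement with its conditions. At SD 0.13, among the plan's rates of decline and slowings of 40% or 60%, 20 per group suffices only for a decline of 0.20 with a 60% slowing. Say whether the 24 completers per group are analysed alone; if so, add that the detectable difference is about 0.107 and power for 0.06 about 35%.
4. **Conservative.** Limit this word to the assumed rate of decline.
5. **Aim 3 (minor).** Restate as about 73% power for 4 points, or 80% for 4.35.

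The cost is a text change in Sections 9.1, 9.3 and 5.1.3, with no new patients, visits or data. If a 40% slowing was intended, the stated power becomes less favourable.

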AP drugs are increasingly prescribed for newly-approved indications including mood disorders and a variety of off-label uses including anxiety, mood stabilization and PTSD (20, 65, 66). For example, in a study of prescribing patterns within the VA, 168,442 of 279,778 individuals (60.2%) who received an AP had no record of a diagnosis for which the drugs were approved(20). In addition to the immediate morbidity attributable to motor symptoms in DIP, APs may act as a “stress test” for the brain revealing subclinical dopaminergic dysfunction such as prodromal PD offering the opportunity for study and

intervention at the earliest stages of disease. The study of disease-modifying therapies in general (and exercise in particular) has been limited by significant dopaminergic denervation already present at motor diagnosis of PD and lack of biomarkers to reliably measure changes in progression. The identification of a prodromal PD cohort will offer the opportunity to study exercise as a symptomatic treatment for DIP and disease-modifying therapy in PD using DaT SPECT as a symptom-independent marker of disease progression.

Section 4: Objectives Section

4.1. Describe the study's purpose, specific aims, or objectives.

AIM 1: To test the effect of regular aerobic exercise on motor function in DIP.

AIM 2: To test whether regular aerobic exercise influences disease progression in prodromal PD

AIM 3: To characterize the mechanism and biochemical correlates of exercise-induced changes in subjects with preclinical PD.

4.2. State the hypotheses to be tested.

Hypothesis 1: Short-term home exercise will improve motor function and could be an effective rehabilitation intervention in DIP.

Hypothesis 2: Exercise subjects will exhibit slower decline in quantitative DaTl, suggesting a disease-modifying effect of exercise in PD.

Hypothesis 3: The relationship of serum markers with clinical and imaging variables will suggest pathways involved in functional changes or disease modification.

Section 5: Study Procedures

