Subjects/Procedures: A cohort of DIP subjects with presumed prodromal PD will be defined by a two-tiered screening procedure. First, DIP subjects will undergo olfactory testing administered by trained study personnel. Subjects with hyposmia (defined as scores below the 25th percentile for age and gender using well-established normative data for the UPSIT) on initial olfactory testing will undergo DaT imaging. We will also recruit subjects with a clinical diagnosis of PD by a PADRECC provider. SPECT scans will initially be read as normal, mildly abnormal or clearly abnormal, in accord with current clinical practice, by a nuclear medicine physician blinded to clinical status. High inter-rater agreement (kappa 0.89-0.93) has been reported for clinical reading of DaT(99). All patients with abnormal (mildly or clearly) DaT SPECT will be referred for clinical follow-up in the PADRECC. The combination of DIP, hyposmia and abnormal striatal DaT imaging will be operationally defined as prodromal PD. All subjects with abnormal olfaction and DaT deficit will undergo baseline motor testing (UPDRS motor and instrumented Timed Up and Go) together with safety screening for exercise. If eligible based on safety screening, baseline cardiovascular fitness testing (VO₂max measurement) will be obtained as described above. Subjects will be then be randomized in a 1:1 ratio to a home-based exercise intervention (5 days/week aerobic walking with confirmation by remote activity monitoring) or no intervention. Subjects will receive weekly phone calls from staff to monitor safety and compliance. After 8 weeks, subjects will undergo repeat clinical (UPDRS motor), quantitative (iTUG) and fitness testing (VO₂max) to examine short-term symptomatic effects of exercise. Eight weeks is a common duration for short-term rehabilitation interventions and was recently reported in a Phase I/II trial of aerobic walking in PD(8).

AIM 2: To test whether regular aerobic exercise influences disease progression in prodromal PD. In this aim, we will test the hypothesis that exercise subjects will exhibit slower decline in semi-quantitative striatal DaT SPECT, suggesting a disease-modifying effect of exercise in prodromal PD.

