Subjects/Procedures: Subjects will be the same prodromal PD cohort described above in Aim 1. Subjects will continue the exercise intervention (or no intervention) for a total of 52 weeks to examine a potential disease-modifying effect. Subjects will continue to receive weekly phone calls from staff to monitor safety and compliance. At the end of the intervention period, control and exercise subjects will undergo repeat DaT SPECT with quantitation of signal in 6 different striatal regions (right and left caudate, right and left anterior putamen, right and left posterior putamen) and repeat exercise testing. If subjects choose to drop out, we will attempt to obtain the final DaT imaging study as soon as possible after notification of the subject's intent to withdraw if they have completed at least 24 weeks of the intervention.

AIM 3: To characterize the mechanism and biochemical correlates of exercise-induced changes in subjects with prodromal PD. In this aim, we will test the hypothesis that serum biomarkers of exercise effects and PD risk will change in the intervention group compared to no intervention.

Subjects/Procedures: Serum biomarkers associated with PD risk or exercise-induced changes (i.e. BDNF, uric acid and apolipoproteinA1) will be measured at baseline, 8 and 52 weeks as described above. The primary outcome of this aim will be differences in the rate of change between intervention groups as assessed using independent samples t-tests. A secondary outcome will examine the rate of change using linear mixed-effects models controlling for age, gender and other potential confounders. Additionally, relationships of biomarkers to VO2max, UPDRS, quantitative motor and quantitative DaT will be examined using partial correlations controlling for age and gender. An intention-to-treat analysis will be applied primarily but pre-planned secondary analyses will compare only exercise subjects deemed compliant with controls.

A schematic demonstrating the flow of recruitment, assessments and analysis is provided below:

[figure not shown]

Figure 3: Overview of study design

5.1.2. What research methods will be used in the project? *Check all that apply.*

 Surveys/Questionnaires	 Interviews	 Audio Taping
 Behavioral Observations	 Chart Reviews	 Video Taping

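### The partial correlations in Aims 1 and 3 omit randomised arm, so pooled estimates would carry a modest between-arm component wherever exercise moves both variables

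*Combined protocol and SAP*

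**What the plan says.** Three sentences specify these analyses.

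- Section 9.2, Aim 1: the association between change in VO2max and change in UPDRS "will be assessed using partial correlations controlling for age, gender and baseline fitness levels".
- Section 9.2, Aim 3: "relationships of biomarkers to VO2max, UPDRS, quantitative motor and quantitative DaT will be examined using partial correlations controlling for age and gender".
- Section 5.1.1, Aim 3, repeats the same covariates: "quantitative DaT will be examined using partial correlations controlling for age and gender".

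None lists randomised arm, and none says that the correlations are run separately by arm. Where section 9.2 intends a by-arm or group-structured analysis, it says so. For Aim 1, "within group changes from baseline for UPDRS scores and quantitative assessments will be assessed using paired t-tests", and the Aim 2 mixed model tests a group-by-time interaction.

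The use to be made of the correlations is given in section 4.2, Hypothesis 3: "The relationship of serum markers with clinical and imaging variables will suggest pathways involved in functional changes or disease modification". Allocation is 1:1 (section 5.1.1, Aim 1: "randomized in a 1:1 ratio to a home-based exercise intervention").

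**The concern.** The trial is designed on the expectation that exercise changes UPDRS, BDNF and DaT, and the exercise programme is meant to raise fitness. Where that expectation is met, assignment is a shared cause of both variables in a correlation. A pooled analysis without arm then mixes two things: the association among subjects within an arm, and the fact that the arms differ on both variables. The listed covariates are measured before randomisation. They are sensible adjustments for confounding between subjects, but they cannot remove a component created by assignment.

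The second component says nothing about a pathway. Two variables that each respond to exercise by unrelated routes produce it just as a true mediator does. The artefact is largest when exercise works, which is also when a pathway statement is most likely to be made. The pooled correlation would then partly repeat the between-group comparisons under the name of mechanism.

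**Working it through.** **Sample size.** Section 9.1, Aim 1, assumes an "effect size (mean(SD)) of a 5.0(7.3) point improvement in UPDRS motor score comparing intervention to control groups" with 80% power. Two-sided alpha of 0.05 is assumed here, since none is printed for Aim 1. The t-based solution is 34.4, so 35 per group, and 35/0.80 = 43.75, so 44 with 20% drop-out. Both printed figures reproduce. The correlations would therefore use about 70 completers, or 48 (24 per group) as expected under the 2018 amendment (section 9.3).

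**Standardised arm effects on change**

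- UPDRS (9.1, Aim 1): 5.0/7.3 = 0.685
- BDNF (9.1, Aim 3): 4/6.4 = 0.625
- DaT, putamen (9.1, Aim 2): (0.15 - 0.09)/0.13 = 0.06/0.13 = 0.46
- VO2max: not given in the documents; 0.5 to 1.5 SD assumed

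These serve only as effect sizes. Nothing below depends on the power statements attached to them.

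**Formula.** With 1:1 arms and zero correlation within arm, the pooled covariance is d1·d2/4 and each pooled variance is 1 + d²/4, so

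|r| = (d1·d2/4) / √[(1 + d1²/4)(1 + d2²/4)]

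BDNF with UPDRS: 0.1070 / √(1.0977 × 1.1173) = 0.097.
BDNF with DaT: 0.0721 / √(1.0977 × 1.0533) = 0.067.

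**False-positive rate.** By Fisher's z, the test statistic is centred at atanh(r)·√(n - k - 3), with k covariates (2 in Aim 3, 3 in Aim 1). For BDNF with UPDRS at n = 70 this is 0.097 × √65 = 0.78. The chance of passing ±1.96 is 11.9% + 0.3% = 12.2%. At n = 48 it is 0.097 × √43 = 0.64, giving 9.7%.

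The simulation used 40,000 trials per case, null covariates, no within-arm link and a two-sided 0.05 test.

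| Pair (change scores) | \|r\| | Fisher z, n = 70 / 48 | Simulated, n = 70 / 48 |
|---|---|---|---|
| BDNF, UPDRS | 0.10 | 12.2% / 9.7% | 12.2% / 9.8% |
| BDNF, DaT | 0.07 | 8.4% / 7.2% | 8.8% / 7.2% |
| VO2max (assumed 0.5 SD), UPDRS | 0.08 | 9.7% / 8.0% | 9.5% / 8.0% |
| VO2max (assumed 0.8 SD), UPDRS | 0.12 | 16.2% / 12.3% | 16.3% / 12.4% |
| VO2max (assumed 1.2 SD), UPDRS | 0.17 | 27.0% / 19.3% | 27.4% / 19.3% |
| VO2max (assumed 1.5 SD), UPDRS | 0.19 | 35% / 25% | not run |
| Marker that exercise does not move, UPDRS | 0.00 | 5% / 5% | 4.9% / 5.0% |

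**With arm as a covariate.** The mean partial r is 0.00 and the rejection rate is 4.8% to 5.2% in every simulated case, at both sample sizes. The last row and this check together show that the inflation comes from the arm effects and from nothing else.

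**If Aim 3 correlates follow-up levels instead of changes.** With the year-1 putamen SD of 0.23 (section 9.1), the DaT effect is 0.06/0.23 = 0.26 SD. Against BDNF at 0.625 SD, |r| is 0.04 and the rate about 6% at n = 70.

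**The case against.** The strongest reply is that the plan is silent on pooling, so a defect is being read into a gap. That stands in part: no sentence states that the arms are pooled. But a single partial correlation with a listed covariate set, in a section that names group structure elsewhere, is most naturally run over everyone. If within-arm analysis was intended, one sentence would settle the matter.

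Second, only Aim 1 says that changes are correlated. Aim 3 does not say whether it uses baseline values, follow-up values or changes. This also stands. Baseline-only correlations would be free of the problem, although the aim concerns changes induced by exercise.

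Third, the stakes are limited. These are additional analyses, and Hypothesis 3 promises only to suggest pathways. That is correct and bears on how serious the point is.

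Fourth, adjusting for arm may discard part of a true mediator's signal. It does remove the between-arm variation. But that variation cannot by itself separate a pathway from two parallel effects, and a real marker-outcome association would still show within arm.

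A reader might go further and infer that any marker responding to exercise will turn out significantly correlated with any outcome responding to it. The documents do not support that. For BDNF with UPDRS, about 88% of analyses with no true link would still be non-significant at 70 completers. The highest rates in the table rest on VO2max effects for which the documents give no basis.

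**Conclusion.** The point holds as a modest, avoidable bias in secondary mechanism analyses. As naturally read, the Aim 1 and Aim 3 partial correlations mix a between-arm component into results that Hypothesis 3 uses to suggest pathways. For pairs whose effects the plan itself gives, the induced |r| is 0.07 to 0.10, and the false-positive rate is about 8% to 12% at 70 completers and 7% to 10% at 48, against a nominal 5%. For VO2max with UPDRS, an assumed 0.5 to 1.5 SD gives |r| of 0.08 to 0.19 and about 10% to 35% at 70, or 8% to 25% at 48.

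This rests on four assumptions: the arms are pooled, change scores are used, exercise has the planned effect on both variables, and there is no within-arm link. The artefact vanishes for any variable that exercise does not move.

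It would be wrong to infer that the treatment comparisons are compromised: the primary t-tests do not involve these correlations. Nor do the documents show that adjusting for age and gender is a mistake. What is missing is arm.

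**What to change.** 1. In section 9.2 (Aims 1 and 3) and in the matching Aim 3 text of section 5.1.1, add randomised arm to the covariates of every partial correlation that uses post-randomisation values or changes.
2. State for Aim 3 which quantities are correlated: baseline values, values at 8 or 52 weeks, or changes between named visits.
3. Base any pathway statement on the arm-adjusted estimate. Say that it remains an observational association within arm and does not establish mediation.
4. Arm-specific correlations may be shown beside it as description.

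The cost is one degree of freedom per analysis and a few sentences of text; no new data are needed. The between-arm variation is given up, which is acceptable because it cannot tell a pathway from two separate responses to exercise.
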